6.3.10 Study Day 28 (Day 28-32)

If the subject is no longer hospitalized, this visit may occur by telephone. In this case, the assessments below should be restricted to the ordinal scale, oxygen requirements, new medical conditions, concomitant medication, and evaluation for AEs.

6.3.10.1 Clinical Data on Day 28

- Vital signs, including SpO₂. These values may be obtained from clinically collected information if they were obtained within 4 hours of the study assessment. Vital signs should be collected in a complete set within 30 minutes of each other.
- Clinical data
 - Assessment of clinical status (6-point ordinal scale)
 - Measures of clinical support:
 - Hospitalization
 - Oxygen requirement
 - Mechanical ventilator requirement
 - ICU requirement
 - ECMO requirement
 - Assessment of ARDS using PaO₂ (or SpO₂), FiO₂, and recent chest x-ray data.
- Review new medical conditions, concomitant medication, and evaluate for AEs

6.4 Special Pregnancy Follow-up Visit

Pregnant subjects should have additional follow-up to evaluate outcomes of the pregnancy. These visits may occur in the hospital, clinic, by chart review, or by telephone, and should occur every month (± 2 weeks, by calendar day of each month) starting one month after discharge until after delivery. The purpose is to assess for SAEs and for pregnancy outcome including gestational age at outcome and live births.

7 MEASURES OF EFFICACY, SAFETY, AND PHARMACOKINETICS

7.1 Pharmacokinetic Measures

Anti-influenza A/H1N1 and A/H3N2 antibodies will be measured by HAI in all subjects on Study Day 0 (pre-infusion), 1, 3, and 7.

7.2 Influenza A Diagnostics - Viral Shedding

OP swabs will be processed to determine quantitative PCR for influenza A.

7.3 Efficacy Measures

7.3.1 Ordinal Scale

The ordinal scale is an assessment of the clinical status at the first assessment of a given study day (i.e., at approximately 8AM). The clinical status should be recorded as the subject currently exists, without consideration as to need (i.e., is the subject in the ICU, and not does the subject have medical needs to be in the ICU, or has the subject been discharged home and not is the subject capable at that moment of being discharged to home). The scale is as follows:

1. Death
2. In ICU
3. Non-ICU hospitalization, requiring supplemental oxygen
4. Non-ICU hospitalization, not requiring supplemental oxygen

5. Not hospitalized, but unable to resume normal activities
6. Not hospitalized with full resumption of normal activities

For the purposes of this study, resumption of normal activities refers to resumption of activities that the subject could undertake prior to first onset of symptom(s) of influenza.

7.3.2 NEW Score

The NEW Score has demonstrated an ability to discriminate patients at risk of poor outcomes. [15] This score is based on 7 clinical parameters. The NEW Score is being used for inclusion criteria, and for efficacy (change from baseline to Day 3 and Day 7). For inclusion criteria, the NEW score is used to define severe influenza. Therefore, the subject must have had a NEW score ≥ 3 within 12 hours prior to randomization. For efficacy, baseline and follow-up days, the score should be calculated as it is at the time of assessment, i.e., no attempt should be made to find the best or worst score in a period of time.

All parameters of the NEW score, including vitals, must be collected as a complete set within 30 minutes of each other. From Day 1 onwards, this should be evaluated at the first assessment of a given study day (i.e., at approximately 8AM). These parameters can be obtained from the hospital chart if performed within 4 hours of the time of assessment, or can be measured at the time of assessment.

Table 6: NEW Score

| National Early Warning Score (NEWS)* | | | | | | | |
|--------------------------------------|-------------|----------|-------------|-------------|-------------|-------------|------------|
| PHYSIOLOGICAL PARAMETERS | 3 | 2 | 1 | 0 | 1 | 2 | 3 |
| Respiration Rate | ≤ 8 | | 9 - 11 | 12 - 20 | | 21 - 24 | ≥ 25 |
| Oxygen Saturations | ≤ 91 | 92 - 93 | 94 - 95 | ≥ 96 | | | |
| Any Supplemental Oxygen | | Yes | | No | | | |
| Temperature | ≤ 35.0 | | 35.1 - 36.0 | 36.1 - 38.0 | 38.1 - 39.0 | ≥ 39.1 | |
| Systolic BP | ≤ 90 | 91 - 100 | 101 - 110 | 111 - 219 | | | ≥ 220 |
| Heart Rate | ≤ 40 | | 41 - 50 | 51 - 90 | 91 - 110 | 111 - 130 | ≥ 131 |
| Level of Consciousness | | | | A | | | V, P, or U |

*The NEWS initiative flowed from the Royal College of Physicians' NEWS Development and Implementation Group (NEWSDIG) report, and was jointly developed and funded in collaboration with the Royal College of Physicians, Royal College of Nursing, National Outreach Forum and NHS Training for Innovation.

Please see next page for explanatory text about this chart.

© Royal College of Physicians 2012

NHS
Training for Innovation

7.3.3 PEW Score

The PEW score is a numerical scoring system to define pediatric patients at risk of clinical deterioration. [16] This score is based on 7 clinical parameters. The PEW Score is being used for inclusion criteria, and for efficacy (change from baseline to Day 3 and Day 7). For inclusion criteria, the PEW score is used to define severe influenza. Therefore the subject must have had a PEW score ≥ 3 within 12 hours prior to randomization. For efficacy, baseline and follow-up days, the score should be calculated as it is at the time of assessment, i.e., no attempt should be made to find the best or worst score in a period of time.

All parameters of the PEW score, including vitals, must be collected as a complete set within 30 minutes of each other. From Day 1 onwards, this should be evaluated at the first assessment of a given study day (i.e., at approximately 8:00 AM). These parameters can be obtained from the hospital chart if performed within 4 hours of the time of assessment, or can be measured at the time of assessment.

Table 7: PEW Score

| Component | Age group | Component subscore | | | |
|-------------------------------|-----------------|--------------------|--------------------------|-------------------------------|-------------------------|
| | | 0 | 1 | 2 | 4 |
| Heart rate, beats/min | <3 months | >110 and <150 | ≥ 150 or ≤ 110 | ≥ 180 or ≤ 90 | ≥ 190 or ≤ 80 |
| | 3 to <12 months | >100 and <150 | ≥ 150 or ≤ 100 | ≥ 170 or ≤ 80 | ≥ 180 or ≤ 70 |
| | 1 to 4 years | >90 and <120 | ≥ 120 or ≤ 90 | ≥ 150 or ≤ 70 | ≥ 170 or ≤ 60 |
| | 5 to <12 years | >70 and <110 | ≥ 110 or ≤ 70 | ≥ 130 or ≤ 60 | ≥ 150 or ≤ 50 |
| | \geq 12 years | >60 and <100 | ≥ 100 or ≤ 60 | ≥ 120 or ≤ 50 | ≥ 140 or ≤ 40 |
| Systolic blood pressure, mmHg | <3 months | >60 and <80 | ≥ 80 or ≤ 60 | ≥ 100 or ≤ 50 | ≥ 130 or ≤ 45 |
| | 3 to <12 months | >80 and <100 | ≥ 100 or ≤ 80 | ≥ 120 or ≤ 70 | ≥ 150 or ≤ 60 |
| | 1 to 4 years | >90 and <110 | ≥ 110 or ≤ 90 | ≥ 125 or ≤ 75 | ≥ 160 or ≤ 65 |
| | 5 to <12 years | >90 and <120 | ≥ 120 or ≤ 90 | ≥ 140 or ≤ 80 | ≥ 170 or ≤ 70 |
| | \geq 12 years | >100 and <130 | ≥ 130 or ≤ 100 | ≥ 150 or ≤ 85 | ≥ 190 or ≤ 75 |
| Capillary refill, s | | <3 | | | ≥ 3 |
| | <3 months | >29 and <61 | ≥ 61 or ≤ 29 | ≥ 81 or ≤ 19 | ≥ 91 or ≤ 15 |
| | 3 to <12 months | >24 or <51 | ≥ 51 or ≤ 24 | ≥ 71 or ≤ 19 | ≥ 81 or ≤ 15 |
| | 1 to 4 years | >19 or <41 | ≥ 41 or ≤ 19 | ≥ 61 or ≤ 15 | ≥ 71 or ≤ 12 |
| | 5 to <12 years | >19 or <31 | ≥ 31 or ≤ 19 | ≥ 41 or ≤ 14 | ≥ 51 or ≤ 10 |
| Respiratory rate, breaths/min | \geq 12 years | >11 or <17 | ≥ 17 or ≤ 11 | ≥ 23 or ≤ 10 | ≥ 30 or ≤ 9 |
| | Normal | Mild increase | Moderate increase | Severe increase/any apnea | |
| | >94 | 91-94 | ≤ 90 | | |
| | Room air | | Any: <4 L/min or <50% | ≥ 4 L/min or $\geq 50\%$ | |

7.3.4 SOFA Score

The SOFA score is a scoring system to determine the extent of a person's organ function or rate of failure. [17, 18] The score is based on six different scores, one each for the respiratory, cardiovascular, hepatic, coagulation, renal, and neurological systems. Baseline assessment should be based on data collected closest to (but also prior to) randomization and plasma administration. Each subsequent day should use the worst value for each parameter in the preceding 24 hour period.

Respiratory System

When using PaO_2 :

$\text{PaO}_2/\text{FiO}_2$ (mmHg)

0 = $\text{PaO}_2/\text{FiO}_2 \geq 400$

1 = $\text{PaO}_2/\text{FiO}_2 < 400$

2 = $\text{PaO}_2/\text{FiO}_2 < 300$

3 = $\text{PaO}_2/\text{FiO}_2 < 200$ and mechanically ventilated

4 = $\text{PaO}_2/\text{FiO}_2 < 100$ and mechanically ventilated

PaO₂ should be used if available. However, if PaO₂ is not available, the following table can be used to generate the SOFA score with SpO₂ [19]:

Table 8: Use of SpO₂/FiO₂ in SOFA Score

| SOFA Respiratory System Points (using SpO ₂) | SpO ₂ /FiO ₂ Ratio | | |
|---|--|-----------|-----------|
| | PEEP < 8 or not intubated | PEEP 8-12 | PEEP > 12 |
| 0 | ≥ 457 | ≥ 515 | ≥ 425 |
| 1 | < 457 | < 515 | < 425 |
| 2 | < 370 | < 387 | < 332 |
| 3 | < 240 | < 259 | < 234 |
| 4 | < 115 | < 130 | < 129 |

Note: The original SpO₂/FiO₂ Ratio as published would require a SpO₂ > 110% to achieve a SOFA score of 0. Therefore, this score has been modified to accept a SpO₂ of 96% or greater on room air as normal (i.e. a SpO₂/FiO₂ Ratio of ≥ 457 would be a SOFA score = 0).

Nervous System

Glasgow coma score

- 0 = GCS score of 15
- 1 = GCS score of 13-14
- 2 = GCS score of 10-12
- 3 = GCS score of 6-9
- 4 = GCS score of < 6

Cardiovascular System

Mean arterial pressure (MAP) OR administration of vasopressors required (vasopressor drug doses are in mcg/kg/min)

- 0 = No hypotension
- 1 = MAP < 70 mmHg
- 2 = dopamine ≤ 5 or dobutamine (any dose)
- 3 = dopamine > 5 OR epinephrine ≤ 0.1 OR norepinephrine ≤ 0.1
- 4 = dopamine > 15 OR epinephrine > 0.1 OR norepinephrine > 0.1

Liver

Total Bilirubin (mg/dL)

- 0 = Total Bilirubin < 1.2
- 1 = Total Bilirubin 1.2 - 1.9
- 2 = Total Bilirubin 2.0 - 5.9
- 3 = Total Bilirubin 6.0 - 11.9
- 4 = Total Bilirubin ≥ 12.0

Coagulation

Platelets $\times 10^3/\mu\text{L}$

- 0 = Platelets $\geq 150 \times 10^3/\mu\text{L}$
- 1 = Platelets $< 150 \times 10^3/\mu\text{L}$
- 2 = Platelets $< 100 \times 10^3/\mu\text{L}$
- 3 = Platelets $< 50 \times 10^3/\mu\text{L}$
- 4 = Platelets $< 20 \times 10^3/\mu\text{L}$

Renal System

Creatinine (mg/dL) (or urine output)

- 0 = Creatinine $< 1.2 \text{ mg/dL}$
- 1 = Creatinine $1.2 - 1.9 \text{ mg/dL}$
- 2 = Creatinine $2.0 - 3.4 \text{ mg/dL}$
- 3 = Creatinine $3.5 - 4.9 \text{ mg/dL}$, or urine output $< 500 \text{ mL/d}$
- 4 = Creatinine ≥ 5.0 , or urine output $< 200 \text{ mL/d}$, or dialysis requirement

7.3.5 PELOD Score

The PELOD score is an organ dysfunction score that can be used in the pediatric population to sequentially evaluate organ dysfunction and predict mortality. Studies have noted that to calculate the PELOD score, each organ dysfunction received points for the variable associated with the highest points. For example, if the worst heart rate of the day was 200 beats/min (10 PELOD points) and systolic blood pressure remained at 30 mmHg (20 PELOD points), then 20 PELOD points were assigned. The maximum number of points for an organ is 20, and the maximum PELOD score 71 [20, 21]. Baseline assessment should be based on data collected closest to (but also prior to) randomization and plasma administration. Each subsequent day should use the worst value for each parameter in the preceding 24 hour period.

Special Considerations for Respiratory Score:

- If blood gas testing was not performed for clinical reasons (e.g., as part of medical care) and the subject is not intubated, it can be assumed that the $\text{PaO}_2/\text{FiO}_2$ ratio is >70 and PaCO_2 is ≤ 90 , and the respiratory score would be 0.
- If the subject is intubated then there will likely be, as part of routine care, an ABG or VBG to determine if the score is 1 or 10 points.
 - A $\text{PaO}_2/\text{FiO}_2$ ratio is ≤ 70 and PaCO_2 is > 90 is very severe disease. If no ABG or VBG is available, the clinical team will be able to estimate if the $\text{PaO}_2/\text{FiO}_2$ ratio is ≤ 70 or PaCO_2 is > 90 based on severity of disease, in which case the respiratory score would be 10.

Table 9: PELOD Scoring System

| Scoring system | | | | |
|---|-------------------------------|----------------------|-------------------------|-----|
| | 0 | 1 | 10 | 20 |
| Organ dysfunction and variable | | | | |
| Neurological* | | | | |
| Glasgow coma score | 12–15 and Both reactive | 7–11 | 4–6 or Both fixed | 3 |
| Pupillary reactions | NA | NA | NA | NA |
| Cardiovascular† | | | | |
| Heart rate (beats/min) | | | | |
| <12 years | ≤195 | NA | >195 | NA |
| ≥12 years | ≤150 and | NA | >150 or | NA |
| Systolic blood pressure (mm Hg) | | | | |
| <1 month | >65 | NA | 35–65 | <35 |
| 1 month–1 year‡ | >75 | NA | 35–75 | <35 |
| 1–12 years‡ | >85 | NA | 45–85 | <45 |
| ≥12 years | >95 | NA | 55–95 | <55 |
| Renal | | | | |
| Creatinine (mg/dl) | | | | |
| <7 days | <1.58 | NA | ≥1.58 | NA |
| 7 days–1 year‡ | <0.39 | NA | ≥0.39 | NA |
| 1–12 years‡ | <1.13 | NA | ≥1.13 | NA |
| ≥12 years | <1.58 | NA | ≥1.58 | NA |
| Respiratory§ | | | | |
| PaO₂ (mmHg)/FIO₂ ratio | >70 and | NA | ≤70 or | NA |
| PaCO₂ (mmHg) | ≤90 and | NA | >90 | NA |
| Mechanical ventilation§ | No ventilation | Ventilation | NA | NA |
| Hematological | | | | |
| White blood cell count (×10⁹/L) | ≥4.5 and ≥35 | 1.5–4.4 or <35 | <1.5 | NA |
| Platelets (×10⁹/L) | NA | NA | NA | NA |
| Hepatic | | | | |
| Aspartate transaminase (IU/L) | <950 and >60 | ≥950 or ≤60 | NA | NA |
| Prothrombin time (or INR) | (<1.40) | (≥1.40) | NA | NA |

Notes:*PaO₂*=arterial oxygen pressure. *FIO₂*=fraction of inspired oxygen.*PaCO₂*=arterial carbon dioxide pressure. *INR*=international normalized ratio.

* Glasgow coma score: use lowest value. If patient is sedated, record estimated Glasgow coma score before sedation. Assess patient only with known or suspected acute central nervous system disease.

† Heart rate and systolic blood pressure: do not assess during crying or iatrogenic agitation.

‡ Strictly less than.

§ If arterial measurement of *PaO₂* unavailable, estimate *fPaO₂/FIO₂* ratio from *SaO₂*. Mechanical ventilation: the use of mask ventilation is not counted as mechanical ventilation. measurement only. *PaCO₂* may be measured from arterial, capillary, or venous samples.

7.3.6 ARDS

The incidence of ARDS will be assessed at each study day using the revised Berlin definition of ARDS. [22]

Table 10: Berlin Criteria for ARDS

| Acute Respiratory Distress Syndrome | |
|-------------------------------------|---|
| Timing | Within 1 week of a known clinical insult or new or worsening respiratory symptoms |
| Chest imaging ^a | Bilateral opacities—not fully explained by effusions, lobar/lung collapse, or nodules |
| Origin of edema | Respiratory failure not fully explained by cardiac failure or fluid overload Need objective assessment (eg, echocardiography) to exclude hydrostatic edema if no risk factor present |
| Oxygenation ^b | |
| Mild | 200 mm Hg < $\text{PaO}_2/\text{FiO}_2 \leq 300$ mm Hg with PEEP or CPAP ≥ 5 cm H ₂ O ^c |
| Moderate | 100 mm Hg < $\text{PaO}_2/\text{FiO}_2 \leq 200$ mm Hg with PEEP ≥ 5 cm H ₂ O |
| Severe | $\text{PaO}_2/\text{FiO}_2 \leq 100$ mm Hg with PEEP ≥ 5 cm H ₂ O |

Abbreviations: CPAP, continuous positive airway pressure; FiO_2 , fraction of inspired oxygen; PaO_2 , partial pressure of arterial oxygen; PEEP, positive end-expiratory pressure.

^aChest radiograph or computed tomography scan.

^bIf altitude is higher than 1000 m, the correction factor should be calculated as follows: [$\text{PaO}_2/\text{FiO}_2 \times (\text{barometric pressure}/760)$].

^cThis may be delivered noninvasively in the mild acute respiratory distress syndrome group.

If PaO_2 is not available, the Manual of Operations (MOP) provides instructions for estimating the $\text{PaO}_2/\text{FiO}_2$ ratio from the FiO_2 and SpO_2 .

The oxygenation assessment should be within 4 hours of the assessment of ARDS. If there is no chest imaging on the day of assessment, the most recent imaging may be used. Subjects meeting all criteria meet criteria for ARDS. Severity should be graded based on the oxygenation in the above table.

7.3.7 Measures of clinical support

At each study day, the following measure of clinical support should be assessed:

- Hospitalization
- Oxygen requirement
- Mechanical ventilator requirement
- ICU requirement
- ECMO requirement

If any of these are present, it should be determined if these are new or ongoing from previous study visits. In the case of a new requirement, the date started should be recorded (not just the date of assessment).

If there were previous interventions that are no longer needed, the date of discontinuation should be noted (not just the date of assessment).

7.3.8 Efficacy Measures Not Used

In IRC002, symptom resolution provided no discriminating power in this population. Additionally, it is notoriously inaccurate, and therefore will not be collected in this study. Most subjects in IRC002 did not have fever, and therefore resolution of fever will not be used in this study.

7.4 Safety Evaluations

As both arms are receiving plasma, the study is not designed to determine the safety of plasma. The safety profile of plasma, however, is well known from decades of transfusions. This study will be able to determine the safety of specific anti-influenza plasma to determine if the rate of AEs is higher, lower, or no different than standard (low-titer) plasma.

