Significant morbidity and mortality from influenza infections occur despite treatment with current antivirals. This randomized, double-blinded, multicenter phase 3 trial will assess the efficacy and safety of high-titer versus low-titer anti-influenza immune plasma in addition to standard care antivirals for the treatment of severe influenza A. Hospitalized subjects with severe influenza A will be eligible for study participation. Up to 40 sites in the United States will participate in this protocol. Adults and children may participate. There is no exclusion for pregnancy.

A total of 150 eligible subjects will be randomized in a 2:1 ratio to receive either high-titer anti-influenza plasma or control (low-titer) plasma. All plasma is from male donors to minimize the risk of TRALI.

Subjects will be assessed on Study Day 0 (baseline) and on Study Days 1, 2, 3, 7, 14, and 28. For participants who are not hospitalized on Days 2, 14, and 28, contact with the participant for the purpose of limited study data collection for those days may be performed by telephone. Study visits on Days 1, 3, 7 must occur in person. All subjects will undergo a series of efficacy, safety, and HAI assessments during the study. Blood samples will be collected on Day 0, 1, 3, and 7. OP swabs for influenza PCR will be obtained on Days 0 and 3.

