12.2 Sample Size and Power Considerations

The planned sample size for the trial is 150 subjects, randomized in an approximately 2:1 ratio to high-titer versus low-titer anti-influenza plasma. To evaluate the power of the study, the following assumptions were made:

- a. The primary analysis will compare the high-titer and low-titer plasmas using a proportional odds model and a two-sided Type I error rate of 0.05.
- b. It is anticipated that very few of these subjects will be randomized and not start study plasma infusion (and so be excluded from the primary analysis) or be lost to follow-up prior to Day 7 (and so have missing data for the primary endpoint). In addition, power is reduced slightly and hence the effective sample size is reduced by interim analyses reviewed by the DSMB. Conservatively, a 10% reduction in the total sample size from 150 to 135 subjects was made to allow for these issues.
- c. Data from the control arm of IRC002 for adults with influenza A infection, NEW score ≥ 3 , and duration of time from onset of symptoms of influenza to randomization ≤ 6 days, suggests the distribution of subjects in the low-titer arm for the primary endpoint shown in the following table:

Table 12: Anticipated Distribution of Subjects in the Ordinal Scale

| | Low-Titer Arm | High-Titer Arm | |
|---|----------------------|-----------------------|-----------|
| | (Based on IRC 002) | 80% Power | 90% Power |
| Died | 10% | 4.3% | 3.7% |
| In ICU | 35% | 20.4% | 18.4% |
| Non-ICU hospitalization, requiring supplemental oxygen | 25% | 23.6% | 22.6% |
| Non-ICU hospitalization, not requiring supplemental oxygen | 10% | 13.3% | 13.4% |
| Not hospitalized, but unable to resume normal activities | 5% | 7.9% | 8.2% |
| Not hospitalized, but with full resumption of normal activities | 15% | 30.6% | 33.7% |
| Proportional odds ratio comparing high titer to low titer | | 2.50 | 2.88 |

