12.3 Statistical Analysis

A detailed statistical analysis plan will be developed before undertaking any comparative analyses of outcomes for the randomized high and low plasma titers. The following provides a brief summary of approach to analysis for the primary endpoint.

As noted above, the primary analysis will use a modified intention-to-treat approach which excludes randomized subjects who do not have an infusion of study plasma started. Statistical inferences will use a two-sided Type 1 error rate of 0.05, and corresponding 95% confidence intervals.

Analysis of the primary endpoint (ordinal outcome of clinical status at Day 7) will use a proportional odds model with an indicator variable for randomized treatment. It is useful to note that the score test of the treatment effect from a proportional odds model is equivalent to a Wilcoxon rank sum test even if the proportional odds assumption does not hold. If there are missing data for the primary endpoint, then sensitivity analyses will be undertaken to evaluate the sensitivity of study conclusions to the handling of the missing data. The proportional odds model will be extended to undertake comparisons of randomized treatments adjusted for variables that might be predictive of the outcome, for example, the ordinal clinical status at baseline. The model will also be extended to evaluate possible differences in the comparison of randomized treatments between subgroups of subjects (treatment by subgroup interaction), including subgroups defined by sex, age (adult/child), race/ethnicity, ordinal clinical status at baseline, NEW score at baseline, and days since onset of influenza symptoms to randomization.

Binary variables such as 28-day mortality, in-hospital mortality, incidence of new ICU admissions, etc., are expected to occur infrequently and will be compared between randomized arms using exact logistic regression. Quantitative variables such as duration of ICU stay and change from baseline in NEW score, etc., are expected to have reasonably skewed distributions and may be subject to censoring (e.g., for subjects in an ICU on Day 28); these will be compared between randomized arms using non-parametric tests (e.g., Wilcoxon's Test adapted, if necessary, to handle censoring).

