Analysis of AE data will primarily be descriptive based on MedDRA coding of events. The proportion of subjects experiencing an SAE and the proportion experiencing a Grade 3 or higher AE will be compared between randomized arms using Fisher's Exact Test.

Analysis of HAI titers will also primarily be descriptive, comparing the geometric mean titers at Days 0, 3, and 7 between randomized arms, to confirm (or otherwise) a difference in titers for subjects receiving high-titer versus low-titer anti-influenza plasma.

For enrolled subjects who were not randomized (i.e. screen failures) or who were randomized but did not receive plasma, the final analysis will detail safety (deaths and SAEs), and reasons they were not randomized or did not receive plasma respectively.

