## **8.2 Serious adverse events (SAEs)**

- a. Table: Number (%) of subjects with an SAE by MedDRA System Organ Class (SOC) and Preferred Term (PT); number (%) of subjects with any SAE. This table will include all SAEs, irrespective of time from randomization to the date of onset of the SAE (i.e. including any SAEs reported after the day of the Day 28 evaluation). A second table will be generated including only SAEs with onset dates through to the day of the Day 28 visit. In these tables, subjects with SAEs will be counted (e.g. counting a subject with multiple SAEs with the same PT only once for that PT).
- b. Table: Number of SAEs by MedDRA System Organ Class (SOC) and Preferred Term (PT); number (%) of SAEs. This table will include all SAEs, irrespective of time from randomization to the date of onset of the SAE (i.e. including any SAEs reported after the day of the Day 28 visit). A second table will be generated including only SAEs with onset dates through to the day of the Day 28 visit. In these tables, SAEs will be counted (e.g. counting multiple SAEs with the same PT within the same subject).
- c. List of SAEs: Randomized arm, subject ID, site, age, pregnancy status, days from randomization to Day 28 visit, days from randomization to SAE, days from start of first infusion to SAE, SAE (MedDRA SOC and PT, and verbatim description), ICH seriousness criterion met, severity grade, relatedness to study intervention, outcome (sort by randomized arm, subject ID, days from randomization to SAE, MedDRA SOC and PT).

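### Protocol 7.4 overstates the safety comparison: about 100 v 50 subjects and no margin cannot establish that AE rates do not differ, and the SAP plans no between-arm estimate for AEs or SAEs

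*Protocol*

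**What the plan says.** Protocol 7.4 (Safety Evaluations) first concedes that, because both arms receive plasma, the trial cannot assess the safety of plasma as such. It then says that the study will be able "to determine if the rate of AEs is higher, lower, or no different than standard (low-titer) plasma". The comparison of high-titer with low-titer plasma on cumulative incidence of Grade 3 and 4 AEs and of SAEs is secondary objective 3 (Protocol 2.2).

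Protocol 12.3 describes the AE analysis as mainly descriptive, then adds one formal comparison: "The proportion of subjects experiencing an SAE and the proportion experiencing a Grade 3 or higher AE will be compared between randomized arms", by Fisher's exact test. The same section says in general terms: "Statistical inferences will use a two-sided Type 1 error rate of 0.05, and corresponding 95% confidence intervals".

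The sample size in Protocol 12.2 is justified on the Day 7 ordinal endpoint alone: "The planned sample size for the trial is 150 subjects, randomized in an approximately 2:1 ratio to high-titer versus low-titer anti-influenza plasma".

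SAP 8.2 and 8.3 plan tables of subjects and of events by organ class and preferred term, totals with any SAE and any AE, and subject listings. They name no between-arm test, difference or interval for SAEs or AEs.

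**The concern.** Determining that two rates do not differ is an equivalence conclusion. It needs a margin stated in advance and an interval narrow enough to fall inside it. Protocol 7.4 claims that ability without qualification, and nothing else in either document supplies the means. Fisher's test looks for a difference and cannot establish that there is none.

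At stake is the safety statement that a Phase 3 report can make on a named secondary objective. A reader who takes 7.4 at face value could expect a reassurance that the design cannot give. The SAP would not correct the impression, because its AE and SAE tables put no uncertainty on the between-arm difference.

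**Working it through.** **Inputs**
- Planned size: 150 at 2:1, so about 100 v 50 (Protocol 12.2). The analysis population requires the infusion to have started, so this is the most that full enrolment can give.
- Smaller case: "Conservatively, a 10% reduction in the total sample size from 150 to 135 subjects was made to allow for these issues", or 90 v 45. That allowance also covers interim analyses and missing Day 7 data, so it is somewhat pessimistic for safety.
- Two-sided 0.05; Fisher's exact test (Protocol 12.3).
- SAE rate: IRC005 states none. As an assumption, the IRC002 rates in Protocol Table 11 are used: 9/46 = 20% with plasma, 19/52 = 37% with standard care, 28/98 = 29% overall. The range is extended to 50%. Neither document gives a Grade 3 or higher AE rate.

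**1. The plan's own power figure.** For the ordinal endpoint, Whitehead's formula gives V = N × (2/9)/3 × (1 − Σp̄³) and power = Φ(√V × ln OR − 1.96). With N = 135 and Table 12's distributions, power is 80.6% at OR 2.50 and 90.3% at OR 2.88, against the stated 80% and 90%. The efficacy calculation reproduces. There is no safety figure to reproduce.

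**2. Precision of the risk difference.** With the same rate p in both arms, the half-width is 1.96 × √[p(1 − p)(1/n₁ + 1/n₂)]. For p = 0.29 at 100 v 50: 1.96 × √(0.29 × 0.71 × 0.03) = 15.4 points.

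| Rate in both arms | 100 v 50 | 90 v 45 |
|---|---|---|
| 20% | ±13.6 | ±14.3 |
| 29% | ±15.4 | ±16.2 |
| 37% | ±16.4 | ±17.3 |
| 50% | ±17.0 | ±17.9 |

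Near-identical observed results, 29/100 v 14/50, give a Newcombe 95% interval of −14.8 to +15.2 points.

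**3. Power of Fisher's test** (exact, enumerating both binomials):

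| Control rate | Excess | 100 v 50 | 90 v 45 |
|---|---|---|---|
| 20% | 10 points | 22.5% | 21.0% |
| 20% | 15 points | 44.4% | 41.1% |
| 20% | 20 points | 68.4% | 62.8% |
| 29% | 10 points | 20.3% | 17.5% |
| 29% | 15 points | 40.3% | 35.6% |
| 29% | 20 points | 63.0% | 58.2% |

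At 100 v 50, a 10-point excess over 29% is therefore non-significant 100 − 20.3 = 79.7% of the time. Power of 80% is reached only at an excess of about 24.5 points (26 at 90 v 45).

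**4. Size needed to exclude an excess.** With 29% in both arms, one-sided 0.025, 80% power and 2:1 allocation, the control arm needs (1.96 + 0.84)² × 0.29 × 0.71 × 1.5 / m². For m = 10 points this is 243, or 729 in total. For 15 points the total is 324, and for 20 points 183. These margins are illustrations; the documents name none.

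**The case against.** The strongest reply is that 7.4 is explanatory text about the choice of control. On that reading it only lists the directions a comparison can take, while the operative objective is to evaluate safety by cumulative incidence. Protocol 12.3 also calls the AE analysis mainly descriptive and promises 95% intervals in general, and by-arm counts in the SAP allow anyone to compute a difference. A 150-subject trial sized on efficacy will always have limited safety precision.

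Much of this stands. A reader might infer that the trial will declare no difference whenever Fisher's p exceeds 0.05. The documents do not say so: 7.4 names no test or decision rule, and 12.3 attaches no such reading to the test. A reader might also infer that Fisher's test on AEs and SAEs is the only safety comparison. It is not: SAP 8.1 plans a Fisher test of in-hospital death, a log-rank test, and a mortality hazard ratio with a 95% interval. The planning rates are borrowed too. IRC002 gave its control arm no plasma, enrolled influenza B, and tabulated SAEs by treatment received.

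The objection does not rescue the wording. A descriptive analysis cannot determine that rates do not differ, so 7.4 and 12.3 pull apart. The general promise of intervals is not carried into SAP 8.2 or 8.3, although the SAP specifies intervals elsewhere (8.1, 10.1, 10.4). The Fisher comparison is missing there as well.

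**Conclusion.** The sentence in 7.4 is wrong as written: it claims a property that the design lacks. At assumed rates of 20% to 50%, the trial will leave differences of about ±14 to 17 points open (±14 to 18 at 90 v 45) even when the observed rates agree. A true 10-point excess over 29% will be non-significant about four times in five. The exact figures depend on the borrowed SAE rates and the derived 100 v 50 split. A lower event rate would narrow the interval in absolute terms (±10.2 points at 10%), but without a margin no width settles the matter.

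The SAP gap is separate and concrete: for SAEs and AEs it gives no between-arm estimate, interval or test, although Protocol 12.3 promises a test.

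Severity is low. Nothing here shows a calculation error or a flaw in the primary analysis, and it is not a case for a larger trial.

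**What to change.** - **Protocol 7.4:** say that the study will estimate the between-arm difference in the proportions with any SAE and with any Grade 3 or higher AE, and that a non-significant result will not be taken as showing no difference. Give any precision figure as a range that depends on the assumed rate and on the numbers infused. If the no-difference verdict is to stay, a margin must be stated in advance.
- **SAP 8.2 and 8.3:** for any SAE and any Grade 3 or higher AE through Day 28, add the risk difference with its 95% confidence interval and the Fisher test from Protocol 12.3. Specify Grade 3 or higher explicitly, because Protocol 10.2 also records lower-grade AEs that lead to plasma discontinuation, so the planned any-AE total is not the same quantity.

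The cost is one protocol sentence and two SAP rows, with no new data or subjects. The safety claim becomes more modest.
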